Subjects will be monitored by their therapist for adverse events for 15 minutes after the patch is applied following the initial application and for an appropriate amount of time following all subsequent applications. Subjects will leave the PT clinic with the patch in place. The patch will be programed to deliver medication over a two-hour period, automatically switching off iontophoresis after the maximum dose has been administered. Subjects will be instructed to remove the patch 2 hours after it has been applied as leaving the patch on longer than the recommended time may increase the risk of skin irritation. Subjects will be instructed to wrap the patch in paper towels and discard the Patch in a receptacle out of reach of children and pets.

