- FACES Pain Scale (see Appendix 12.2) a patient reported paper-based questionnaire that asks the patient to choose the face that best represents the pain they are experiencing in their knee. Assessed at the end of each Study Treatment Visit and again at the end of the Clinic Check Visit.
- RTS Criteria Checklist (see Appendix 12.3) a paper-based checklist completed by the Treating
 Therapist to determine whether or not the participant is ready to safely return to sport. The
 checklist was created to include the basic movements typically required for sports activities,
 though these activities are also applicable for return to PE participation and free play, making it
 appropriate for all patients, even those not involved in organized sports. These movements
 include squatting, running, bilateral and unilateral jumping, back pedaling, and quick direction
 changes. The checklist includes qualifying criteria for proper mechanics and requires that all
 activities be pain-free. The checklist was created to assess readiness for sports participation
 without actually requiring that the patient return to sport participation to meet criteria, as not
 all patients participate in organized sports or are in-season year round. The items assessed as
 part of this checklist are all part of normal standard of care for physical therapy. Assessed at
 each Study Treatment Visit and again at the Clinic Check Visit.
- Godin Leisure-Time Exercise Questionnaire (see Appendix 12.4) a paper-based subject self-reporting questionnaire comprised of four (4) items that address the amount of time an individual engages in mild, moderate, and strenuous leisure time physical activity of at least 15 minutes in duration during a typical week. Assessed at Study Treatment Visit 1 and at the 30-day phone follow-up (see Appendix 12.5 30-Day Phone Follow Up) and 90-Day Follow-Up (see appendix 12.6 90-Day Follow-Up Electronic Survey).
- Study Treatment:
 - Iontophoresis (Groups A and B only) ~ 3 minutes in clinic and 2 hours at home The iontophoresis patch will be applied by a trained therapist in blinded fashion for all participants assigned to groups A and B (see section 6.1.2 Dosing and Administration). Performed at Study Treatment Visits 1 12 (Maximum of 12 treatments, maximum of 8 weeks since first Study Treatment Visit, or when RTS criteria are met and confirmed at the Clinic Visit Check, whichever is sooner).

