 - For subjects assigned to Group "C" (PT only Group), Study Treatment Visits 1 12 (maximum of 8 weeks since first Study Treatment Visit, or when RTS criteria is met) will

include only their standard PT Treatment Visits: Study Treatment 1 = Standard PT Treatment 1, Study Treatment 2 = Standard PT Treatment 2....).

Note: Participants who initially meet RTS Criteria but fail to meet the RTS criteria when they return for their Clinic Visit Check will continue with their assigned study treatment until the sooner of: they once again achieve RTS criteria, they have received 12 study treatments, or they have received study treatment for eight (8) weeks.

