8.2 SAFETY AND OTHER ASSESSMENTS

The following procedures/evaluations will be obtained by qualified Therapists treating the subjects: Assessed At Enrollment/Randomization Study Treatment Visit 1:

 Inclusion/Exclusion Criteria - Based on the patient's medical history and review of the initial evaluation, the Treating Therapists will determine whether patients meet eligibility criteria for the study.

Note: if radiograph images were obtained to determine skeletal maturity, the Treating Therapist will ensure the results are documented in the radiologist's notes or noted in the physician's notes in the electronic medical record.

- Informed Consent Treating Therapist will conduct the informed consent process as outlined in Section 10.1.1.2 of this document.
- Randomization After a patient signs Consent, the Treating Therapist will assign the patient to the research group per the randomization log at the Site (see section 6.3 Measures to Minimize Bias: Randomization and Blinding).

Assessed at All Study Treatment Visits:

- Brief Physical examination of the affected knee an evaluation made by the treating physical therapist to include: skin color, temperature, presence of edema, turgor, pain with palpation/pressure, changes to skin texture, and integrity. Also assessed at Clinic Check visit.
- Concomitant Medication Review a paper-based form completed by the Treating Therapist to document drug, dose, frequency, start and stop dates, and reason for taking. Also assessed at Clinic Visit Check visit.
- Adverse Event Evaluation a paper-based form completed by the Treating Therapist to document occurrence, severity, relatedness, duration, and expectedness of the event. Subjects receiving iontophoresis will be specifically monitored for possible burns. This data will be captured during the examination of the affected knee as well as for 15 minutes post patch application.

Also assessed at Clinic Visit Check visit, 30-Day Phone Follow Up and electronically at the 90-Day Follow Up (see Appendix 12.6 90-Day Follow Up – Electronic Survey)

• Compliance Checks – a paper-based form completed by the Treating Therapist to assess participant compliance with: study visits, length of time iontophoresis patch worn, home exercise program, icing, activity restriction, and bracing instructions. Also assessed at Clinic Check visit.

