9.4.3 ANALYSIS OF THE SECONDARY ENDPOINT(S)

For each secondary endpoint:

A Generalized Estimation Equation (GEE) Model, including baseline records, will be used to check for changes in LEFS, FACES pain scale, and Godin Leisure-Time Exercise between treatment groups over time. Results for LEFS and Godin Leisure-Time Exercise will be presented as mean with 95% confidence interval, and results for FACES pain scale will be reported as odds ratio and 95% confidence interval.

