9.4.5 BASELINE DESCRIPTIVE STATISTICS

Age at admission and baseline patient reported outcomes will be compared between treatment groups using Analysis of Variance (ANOVA) test. Chi-square test will be conducted to test comparability of intervention groups in terms of gender and race distribution. Continuous variables will be presented as mean and standard deviation. Categorical variables will be expressed as frequency and percentage. All tests will be two-sided and p < 0.05 will be considered statistically significant.

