12.2 WONG BAKER FACES PAIN SCALE

12.3 RETURN TO SPORT CHECKLIST

Phase 1 - Nonimpact

. Pain-free ADL's

□Squats x 10 pain-free with proper mechanics (all of the following must be met:)

□No anterior tibial translation

□ Heels stay in contact with the ground

□Neutral/slight external rotation foot placement

 \Box Knee stays in line with 2nd toe

□Trunk upright

□No trunk shift

NOTE: Must meet both Phase 1 criteria before progressing to Phase 2 criteria. Phase 2 criteria must be assessed/completed in the order listed below.

Phase 2 - Impact

Broad jumps x10 pain-free with proper mechanics (all of the following must be met:)

□Knee in line with 2nd toe on take-off and landing

□No anterior tibial translation on landing

□Even footing on take-off and landing

□Soft landing

□ Pain free

□Single leg triple hop for distance (all of the following must be met:)

□ Met all above criteria for broad jumping

 \Box No loss of balance

 \Box No extra hop on landing

□No touching down of either the contralateral lower extremity or the upper extremity

□Stick and hold final landing for at least 3 seconds

□Affected lower extremity within 85% of the unaffected lower extremity

□ Pain-free

□ Modified T-test

□ Met all above criteria for single leg triple hop for distance

 \Box 100% effort

 \Box Pain-free

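### The first FACES pain score comes after randomisation and the start of treatment, so the FACES baseline that the analysis relies on is a post-randomisation value

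*Combined protocol and SAP*

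**What the plan says.** FACES is a named secondary efficacy endpoint. On its timing, 8.1 says: "Assessed at the end of each Study Treatment Visit and again at the end of the Clinic Check Visit". The Schedule of Activities (1.3) has its first FACES mark at Visit 1 and none at the Initial Evaluation.

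Three things happen at Visit 1:

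- **Randomisation.** Section 8.2: "After a patient signs Consent, the Treating Therapist will assign the patient to the research group per the randomization log at the Site".
- **First PT session.** For Group C, 8.1 states "Study Treatment 1 = Standard PT Treatment 1". Section 4.1 gives the standard PT protocol to all three groups.
- **First patch, Groups A and B.** Section 8.1 describes iontophoresis as "Performed at Study Treatment Visits 1" to 12. Section 6.2.4 adds: "Subjects will leave the PT clinic with the patch in place".

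The analysis then calls on a baseline. In 9.4.3 a GEE, "including baseline records, will be used to check for changes in LEFS, FACES pain scale" and the Godin questionnaire, compares the groups over time, with FACES reported as an odds ratio. In 9.4.5: "Age at admission and baseline patient reported outcomes will be compared between treatment groups", by ANOVA. Neither section says which FACES record is the baseline.

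**The concern.** A baseline earns its place because allocation cannot have affected it. Randomisation then makes its expected difference between arms zero, so it can be used to adjust or to anchor change. A score taken at the end of Visit 1 lacks that property. The child has been allocated, has had a PT session, and knows whether a patch is part of treatment.

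Two consequences follow. First, the 9.4.5 comparison would no longer describe the groups as randomised, because an imbalance could be an early response to treatment or to knowing the allocation. Second, any early between-arm difference in the Visit 1 score is carried into the 9.4.3 comparison as if it had existed before treatment.

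The documents give reasons to take this seriously. Section 2.3.1.1 lists tingling, prickling and warmth as normal with iontophoresis, and 4.2 justifies the control groups by a high placebo effect in children. Group C receives no patch and knows it (6.3).

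**Working it through.** There is no planned figure for FACES timing to reproduce, so the check sets the sections side by side and then does one piece of arithmetic on the device settings.

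1. **Order of events at Visit 1.** Consent comes first, then randomisation (8.2). PT and, in Groups A and B, the patch belong to the same visit (8.1). FACES is at the end (8.1). The score is therefore after randomisation and after the PT session. It is probably after patch application too, but no section orders FACES and the patch within the visit.

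2. **Is there an earlier value?** The standard-of-care Initial Evaluation includes a pain assessment (8.1). It is not named as FACES, and the schedule marks no FACES there. It cannot serve as the FACES baseline without a change to the plan.

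3. **What a post-randomisation baseline does to the estimate.** Let d0 be the between-arm difference (log odds ratio) in the Visit 1 score and dt the difference at a later visit.
 - If Visit 1 is the time-zero response, the group-by-time contrast is dt − d0.
 - If it is a covariate with slope b, the adjusted contrast is about dt − b × d0.
 - With a pre-randomisation score, d0 has expectation zero and neither contrast is biased by it. With an end-of-visit score, d0 need not be zero.
 - If the patch lowers early scores through expectation, a later benefit over PT alone is understated. If sensation under the patch raises early scores, it is overstated. The sign is not known.

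4. **Which comparison is exposed?** Section 6.1.1 gives 3 mA for 3 minutes, then 0.67 mA for 120 minutes.
 - Charge: 3 × 3 = 9 mA-min, and 0.67 × 120 = 80.4 mA-min, which agrees with the 80 mA-minute dose in 6.2.4. Total 89.4 mA-min.
 - At controller removal: 9 / 89.4 = 10.1%.
 - After the 15-minute watch (6.2.4), if it starts at removal: (9 + 15 × 0.67) / 89.4 = 19.05 / 89.4 = 21.3%.
 - If the 15 minutes include the 3-minute phase: (9 + 12 × 0.67) / 89.4 = 17.04 / 89.4 = 19.1%.
 - Against a full course of 12 patches: 21.3% / 12 = 1.8%.

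 If drug delivery is roughly proportional to charge (an assumption), little DSP has been delivered by the end of Visit 1. Both iontophoresis arms also have the same patch, current and PT under blinding (6.3). For DSP versus saline, d0 should be close to zero. For either iontophoresis arm versus PT alone, sensation and expectation differ and d0 is unknown.

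5. **Can the bias be sized?** No. The documents give no FACES variance, no expected early difference and no effect size for pain. Section 9.2 gives 87 participants for patient-reported outcomes without the inputs behind that figure.

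**The case against.** **The baseline is undefined rather than wrong.** Sections 9.4.3 and 9.4.5 do not say that the Visit 1 score is the baseline, and a pain assessment exists at the Initial Evaluation. This stands in part: use of the Visit 1 score is the natural reading, not a stated one. But it is the earliest FACES value the plan collects, and its timing is a stated rule, so this is more than a missing detail.

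**The score might be taken before the patch.** This stands. A reader might infer that the current is always running when the child is scored, but the text says only that scoring is at the end of the visit. Scoring after exercise and before the patch also fits. The score would still follow randomisation and PT.

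**The main drug question is barely touched.** This also stands, for the reasons in the arithmetic on charge. The exposure lies mainly in comparisons with PT alone.

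**End-of-session scoring suits this condition.** Pain is worse after activity (2.1), and pain on palpation alone is an exclusion (5.2). A score before exercise could sit near the floor. This is a fair defence of the later scores, and the point does not ask for them to be moved.

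**Conclusion.** The point holds for the baseline only. As written, the first FACES record follows randomisation and the first PT session, and in Groups A and B probably the first patch application. The plan relies on a baseline that it has not collected before allocation. The primary endpoint is unaffected. The conclusion assumes that 9.4.3 and 9.4.5 would draw on the earliest scheduled FACES record, since no other is available.

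Neither the size nor the direction of the bias can be derived from the documents. Two stronger readings are tempting and are not supported:

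- *A definite share of the treatment effect is already in the Visit 1 score.* No figure in the documents supports a share, and little DSP-specific effect can be present by then.
- *Later scores penalise the arm that improves faster, because impact tasks come only to children who progress.* The checklist in 12.3 does gate them: "Must meet both Phase 1 criteria before progressing to Phase 2 criteria". But Phase 2 items must be pain-free to pass, a child who fails Phase 1 may fail because of pain, and the PT exercises are not in the documents. The net effect could go either way.

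**What to change.** In 8.1 and the Schedule of Activities, add one FACES score at Visit 1, after consent and before randomisation, exercise, the RTS checklist and the patch. Define it in 9.4.3 and 9.4.5 as the FACES baseline.

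Keep all end-of-visit scores, including that of Visit 1, as post-baseline outcomes. In the 9.4.3 model, enter the new score as a covariate rather than as a time-zero response, because it is taken before exercise and the later scores are taken after it.

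The cost is one extra brief questionnaire per child and a reordered Visit 1 worksheet, with no added visit. Scoring after consent respects the rule in 8.1 that study procedures never precede it.

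The downside is that children already enrolled have no such value. The amendment history (10.3) suggests that there may be some. Their Visit 1 score must be labelled post-randomisation and not used as baseline, and the plan should state how the missing covariate is handled for them.

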8.2 SAFETY AND OTHER ASSESSMENTS

The following procedures/evaluations will be obtained by qualified Therapists treating the subjects: Assessed At Enrollment/Randomization Study Treatment Visit 1:

 Inclusion/Exclusion Criteria - Based on the patient's medical history and review of the initial evaluation, the Treating Therapists will determine whether patients meet eligibility criteria for the study.

Note: if radiograph images were obtained to determine skeletal maturity, the Treating Therapist will ensure the results are documented in the radiologist's notes or noted in the physician's notes in the electronic medical record.

- Informed Consent Treating Therapist will conduct the informed consent process as outlined in Section 10.1.1.2 of this document.
- Randomization After a patient signs Consent, the Treating Therapist will assign the patient to the research group per the randomization log at the Site (see section 6.3 Measures to Minimize Bias: Randomization and Blinding).

Assessed at All Study Treatment Visits:

- Brief Physical examination of the affected knee an evaluation made by the treating physical therapist to include: skin color, temperature, presence of edema, turgor, pain with palpation/pressure, changes to skin texture, and integrity. Also assessed at Clinic Check visit.
- Concomitant Medication Review a paper-based form completed by the Treating Therapist to document drug, dose, frequency, start and stop dates, and reason for taking. Also assessed at Clinic Visit Check visit.
- Adverse Event Evaluation a paper-based form completed by the Treating Therapist to document occurrence, severity, relatedness, duration, and expectedness of the event. Subjects receiving iontophoresis will be specifically monitored for possible burns. This data will be captured during the examination of the affected knee as well as for 15 minutes post patch application.

Also assessed at Clinic Visit Check visit, 30-Day Phone Follow Up and electronically at the 90-Day Follow Up (see Appendix 12.6 90-Day Follow Up – Electronic Survey)

• Compliance Checks – a paper-based form completed by the Treating Therapist to assess participant compliance with: study visits, length of time iontophoresis patch worn, home exercise program, icing, activity restriction, and bracing instructions. Also assessed at Clinic Check visit.

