6.3 MEASURES TO MINIMIZE BIAS: RANDOMIZATION AND BLINDING

A center-stratified randomization method will be used to maintain balance between treatment groups and centers. Equal number of participants per intervention will be considered to maximize study power. The CHKD Pharmacy Department will hold the randomization key and will prepare bottles of study drug and placebo (see Section 6.2.2 Formulation, Appearance, Packaging, and Labeling).

Treating therapists will assign randomization codes in chronological order as participants enroll in the study. Since the study drug and sodium chloride are identical in appearance, the Treating Therapists will

be blinded to study assignment. Those participants assigned to "Group C", or standard PT alone, will be unblinded to treatment as they will not receive iontophoresis.

In the case of an unexpected and serious adverse event in which knowing the study assignment is critical to the medical care of the participant, the CHKD pharmacist may release this information to the Independent Safety Monitor only, who may share this information with the treating physician.

Both the Treating Therapist and the participants assigned to one of the two iontophoresis groups will be blinded to study treatment. The DSP injection and 0.9% sodium chloride injection are clear, colorless liquids that will be supplied by the CHKD Pharmacy Department in identical looking single-use bottles. Each bottle will contain 1.8 mL of solution and will be labeled in a blinded fashion as either lontophoresis Study Drug "A" or "B".

In this study, the Treating Therapists will also perform all physical therapy assessments. While having a separate group of "assessing therapists" and "treating therapists" minimizes bias even further than the current study design, combining their roles is preferred as it reduces error by minimizing the number of therapists involved, improves completion consistency of the RTS Criteria Checklist, and minimizes scheduling conflicts caused when trying to coordinate two therapist's schedules for every study visit conducted.

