10.1.1.2 CONSENT PROCEDURES AND DOCUMENTATION

Patients seen by CHKD Primary Care Sports Medicine physicians or CHKD Orthopedic physicians with a diagnosis of apophysitis of the knee and referred to CHKD PT for PT treatment and iontophoresis treatment will be potential subjects for the study. The referring physician will provide written approval to the Treating Therapist that the patient may be considered for enrollment into this study. The referring physician may provide an IRB-approved Informational Flyer to the parent and child for their review prior to meeting with the Physical Therapist. The Principal Investigator's (PI) contact information will be provided on the Informational Flyer. Parents may choose to call the PI to discuss the study or request that the informational packet be emailed or mailed to them in advance of their IE Visit.

As standard of care, all patients referred for PT treatment and iontophoresis receive an IE in one of the CHKD PT clinics. After the Treating Therapist receives the referral and prior to the IE, the Treating Therapist will ensure the referring physician has provided written approval for the patient to be

considered for enrollment in the study. Once approval is secured, the Treating Therapist may contact the parent to discuss the study and answer any questions they may have. At the IE, the Treating Therapist will discuss the study with the patient and his/her parent/legally authorized representative (LAR) in detail and if interested in participating in the study, will provide them a copy of the IRB-approved informed consent and assent forms for review.

Patients will have the opportunity to carefully review the written consent form and ask questions prior to signing. The patients will have the option to sign Consent on the day of the IE or take more time to consider it and decide at the beginning of their next Standard PT Treatment visit.

Informed consent will only occur at the PT clinics and will be conducted by the Treating Therapists who have been CITI trained. The Informed consent process will be initiated prior to the individual's agreeing to participate in the study and will continue throughout the individual's study participation. No study-specific procedures will be conducted until the Consent and Assent Forms are signed and dated.

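### Nothing in the plan requires the next assignment to be hidden from the therapist who judges eligibility, takes consent and assigns, so the PT-alone comparison is not protected against selection

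*Combined protocol and SAP*

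**What the plan says.** Section 8.2 gives the Treating Therapist the eligibility decision: "the Treating Therapists will determine whether patients meet eligibility criteria for the study". Section 10.1.1.2 gives the same role the consent discussion: "Informed consent will only occur at the PT clinics and will be conducted by the Treating Therapists who have been CITI trained". Assignment follows, again by that role: "After a patient signs Consent, the Treating Therapist will assign the patient to the research group per the randomization log at the Site". Section 6.3 adds the order: "Treating therapists will assign randomization codes in chronological order as participants enroll in the study". It also has the Treating Therapists perform all physical therapy assessments, which include the RTS checklist behind the primary endpoint.

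On protection, section 6.3 says "The CHKD Pharmacy Department will hold the randomization key", and sections 6.2.1 and 6.2.2 describe identical bottles labelled A or B. Group C has no bottle. Section 6.3 says that participants in group C, "or standard PT alone, will be unblinded to treatment as they will not receive iontophoresis".

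On timing, section 10.1.1.2 allows contact before the initial evaluation: "Once approval is secured, the Treating Therapist may contact the parent to discuss the study". A family may sign that day or "take more time to consider it and decide at the beginning of their next Standard PT Treatment visit".

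The plan mentions no sealed envelopes, no central or web release and no restricted access to the clinic log. The one log with stated restricted access is the pharmacy compounding log (section 6.2.1), which protects A versus B.

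**The concern.** Concealment of the next assignment is separate from blinding after assignment. Here blinding covers only A versus B. A therapist who can foresee that the next slot is C could, knowingly or not, influence which child fills it, by the timing of the consent discussion or by how eligibility is judged. The plan as written permits this and does not guard against it.

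There is a plausible reason to prefer a patch slot. Every candidate arrives with a prescription that includes iontophoresis (section 5.1), and section 2.3.3 reports long and favourable clinical experience with it.

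The stake is the primary test. PT alone is a comparator in the primary hypothesis (section 9.1), so a prognostic difference between C and the patch arms enters it directly. The direction cannot be predicted: slower-recovering children moved to the patch would count against iontophoresis, and faster-recovering children in its favour.

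The planned analyses would reveal some of this but not remove it. Section 9.4.5 compares age, gender, race and baseline patient-reported outcomes between arms. The covariate model for time to RTS in section 9.4.6 includes age, gender, race and concomitant therapies, but not baseline LEFS or FACES. An imbalance in baseline function or pain would therefore be seen but not adjusted for on the primary endpoint. The secondary GEE models do include baseline records (section 9.4.3).

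**Working it through.** **1. Which step hides what**

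| Safeguard | DSP vs placebo | Patch vs PT alone, next slot |
|---|---|---|
| Pharmacy key, identical bottles (6.2.1, 6.3) | hidden | not addressed |
| Assignment after consent (8.2) | – | fixes the order of steps, not what can be foreseen |
| Physician approval (5.1), Screening Log (5.5), full review of consent and eligibility forms (10.1.6) | – | limit or help expose steering; do not hide the slot |

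**2. The plan's own figure.** Section 9.2 gives N = 126 for f = 0.28, 80% power and α = 0.05. A three-group F test with noncentrality λ = N·f² gives power 0.8002 at N = 126, so the figure reproduces. At N = 147 power is 0.862. Concealment changes neither number.

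**3. Opportunity.** Inputs are 147 children, 40 months and six clinics (section 1.1).
- Accrual: 147/40/6 = 0.6125 per clinic per month, or one child per 30.44/0.6125 = 49.7 days.
- Assuming even Poisson arrivals, P(next child at the same clinic within w days) = 1 − exp(−w/49.7). Multiply by the 49 C slots, then by 2/3 because an exchange matters only if the next slot is a patch.

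| Window w | Probability | C slots (×49) | Usable (×2/3) |
|---|---|---|---|
| 3.5 days | 6.8% | 3.3 | 2.2 |
| 7 days | 13.1% | 6.4 | 4.3 |
| 14 days | 24.5% | 12.0 | 8.0 |

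At most two sessions a week (section 6.1.1) makes 3.5 days a rough gap to the next visit. The 7- and 14-day windows are assumptions. Uneven clinics, candidates who decline, and pairs where the patch slot comes first would raise the counts.

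**4. Effect on the false-positive rate.** Assumptions not in the documents: no true effect, 49 per arm, and k exchanges between C and the 98 patch children, spread evenly over A and B, with each pair differing by d SD.
- Shift between patch and C = k·d/49 + k·d/98
- f = shift·√2/3; λ = 147·f²; F(2,144) critical value 3.059

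| k | d | Shift (SD) | f | Rejection rate |
|---|---|---|---|---|
| 2 | 0.5 | 0.031 | 0.014 | 5.2% |
| 2 | 1.0 | 0.061 | 0.029 | 5.9% |
| 4 | 0.5 | 0.061 | 0.029 | 5.9% |
| 4 | 1.0 | 0.122 | 0.058 | 8.8% |

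Two and four are the usable counts at 3.5 and 7 days, rounded, with every opportunity taken.

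**5. Stress tests.** Six exchanges give 7.1% to 14.0%, but six exceeds the 4.3 usable slots at 7 days. For power, take f = 0.28 at N = 147 (86%) and three exchanges of slower children to the patch. Power falls to 80–72% if both patch arms beat C by 0.28·3/√2 = 0.594 SD, but only to 83–81% if DSP alone is better by that amount. Steering the other way raises power above 86%.

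**The case against.** The strongest reply is that the documents show silence, not exposure. Section 6.3 speaks of codes in the clinics and a key in the pharmacy, so the log may already be masked, and the working detail may sit in site or pharmacy procedures. Section 6.2.4 has the therapist fetch the labelled bottle once a child is randomized, and knowing a letter after assignment is not knowing the next one beforehand. This stands. A reader might infer that therapists can read the list or that children are being steered, and the documents support neither.

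The reply does not dispose of the point. The therapist must learn A, B or C to act on it, the stated procedure is that the enrolling person assigns from a list at the clinic, and no rule says when an entry becomes visible. Followed to the letter, the plan allows foreknowledge of C slots.

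A second reply concerns size. It is tempting to quote an error rate near 14% or power near 72%. The first needs more exchanges than the 7-day count supplies; the second needs a placebo patch that works as well as DSP, together with one direction of steering. Even the smaller figures assume that every opportunity is used and that each pair falls in the wanted prognostic order. The choice of consent day also belongs to the family. These limits are accepted, so the larger figures serve only as stress tests.

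Third, the scope is narrow: DSP versus placebo stays protected while the A/B code is unbroken, and group C is openly unblinded by design. That is correct. Openness after assignment, however, is a reason to conceal the assignment beforehand, not a substitute for doing so.

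**Conclusion.** The point holds as a gap in the plan. One role judges eligibility, takes consent, assigns in order from a clinic log and scores the outcome, and no text requires the next entry to be hidden. The exposure is confined to patch versus PT alone, which forms part of the primary hypothesis.

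The size and direction of any bias cannot be derived, because the documents give no SD and no steering rate. Under the stated assumptions, two to four exchanges move the false-positive rate from 5% to between 5.2% and 8.8%. That is modest, but it is avoidable at small cost, and concealment cannot be restored afterwards for children already assigned. Whether the existing log is masked is the one fact that would reduce this to a matter of wording.

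**What to change.** In sections 6.3 and 8.2, replace assignment from a clinic-held log with release of each assignment only after eligibility and signed consent are recorded. Two routes would serve:
- The pharmacy, which already holds the key, prepares sequentially numbered, opaque, sealed envelopes for each clinic, opened after consent and signed with date and time.
- A central or REDCap release, if available. Section 10.1.8.1 shows REDCap for data capture, but no section shows a randomization module.

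State that no clinic holds a readable list. Keep stratification by clinic; if blocks are used, vary their size and do not disclose it to the clinics. For partly used clinic sequences, seal the unused remainder if staff have not seen it; otherwise have the pharmacy generate a new remainder that keeps the arms balanced.

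For participants already assigned, have the monitors compare log order with consent dates and the Screening Log at each clinic, and report the result.

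If the present log already conceals its entries, keep it and say how in one or two sentences. Otherwise the cost is up to 147 envelopes plus spares or a one-off system set-up, brief training, a few minutes at Visit 1 and a short amendment. Bottles, labels, visits and sample size do not change.
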